Research Proposal

04/08/2021

Study Title: SCI Step Together: Improving Physical Activity Participation Among Individuals With SCI Who Ambulate

Primary Investigator: [name] [name] (University of British Columbia)

Co-investigators: [name] (University of British Columbia)

Study Sites: 1. University of British Columbia, Kelowna, BC, Canada

Sponsors: Social Sciences and Humanities Research Council
WorkSafe BC Research Training Award
CDPP Funding

SUMMARY

Purpose: To assess the feasibility and acceptability of a mobile health application (mHealth app) to increase quantity and quality of physical activity experiences among ambulators living with spinal cord injury.

Justification: Individuals living with spinal cord injury (SCI) who walk participate in less physical activity than individuals with SCI who use wheelchairs. Lower levels of physical activity may be due to barriers such as increased pain and fatigue, lack of time, and lack of knowledge. Additionally, in the second study of my dissertation, we identified that action and coping planning, goal conflict, and skills are associated with increased physical activity levels. Quality of physical activity experiences also play an important role in participation. Recently, elements of positive and negative physical activity experiences, in addition to factors that influence quality, were classified among individuals with SCI who ambulate in the third study of my dissertation. These elements mapped onto the Quality Participation Framework (i.e., autonomy, belongingness, challenge, engagement, meaning, mastery) and the conditions aligned with the Quality Parasport Participation Framework (intrapersonal, social, program, and physical). Despite the recent focus on understanding factors that enhance both quantity and quality of physical activity participation, there are no physical activity interventions available targeted specifically for individuals with SCI who walk. Therefore, this study will develop and assess the acceptability and feasibility of a mHealth app to increase the quantity and quality of physical activity among ambulators with SCI according to evidence from the previous two studies.

Objectives: The main objectives are to: (a) collaboratively develop and implement the 8-week program delivered through a mHealth app, (b) qualitatively evaluate the subjective experiences of the mHealth program (i.e., engagement, acceptability, and feasibility) and (c) quantitatively evaluate the engagement, acceptability, and feasibility, in addition to behaviour change factors, leisure-time physical activity levels, quality of physical activity participation, and employment.

Study Design/Methods: This randomized controlled trial (RCT) will recruit a total of 20 ambulators with SCI across Canada and the United States. Consenting participants will be randomized into either the wait-list control or intervention group. The wait-list control group will be asked to continue their everyday routine and not engage in any new physical activity or health program. The intervention group will participate in an 8-week program (also termed intervention) delivered through a mHealth app, consisting of education modules, worksheets, peer support and behavioural support. The intervention will aim to increase physical activity quantity and quality. Assessments will take place at baseline, 4-weeks, and 8-weeks for both the control and intervention groups. These assessments include social support, action control, basic psychological needs, autonomous motivation, behaviour change domains, leisure-time physical activity, quality of exercise and sport experiences, and employment hours and financial resources. After completing the final assessments at 8-weeks, participants in the intervention group will be invited to participate in an interview to get a better understanding of their satisfaction with the program. Only investigators on the study will have access to the de-identified data, which will be stored on a password-protected folder in UBC's One Drive.

Analyses: Demographic information will be used to describe the sample. Descriptive statistics will be used to characterize the sample using means and standard deviations for continuous variables and proportions and frequencies for categorical variables. Mixed effect models will be used to test for statistically significant different ($p<0.05$) in quantitative outcomes. Qualitative interviews will be transcribed, and a content analysis of the interview transcripts will be guided by an inductive approach.

Table of Contents

1. SUMMARY.....	2
2. BACKGROUND AND PROGRAM RATIONALE.....	5

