Hypotheses: The primary hypothesis is that the program will be deemed an acceptable and feasible method of improving physical activity participation among individuals with SCI who ambulate. A secondary hypothesis is that the program will improve basic psychological needs and autonomous motivation to participate in LTPA. A tertiary hypothesis is that the program will increase leisure-time physical activity levels, quality of physical activity participation, and employment.

2. MEASURES (Appendix A)

The following section on Feasibility and Engagement will not require any additional effort or information from participants, but rather assesses the study progression to understand whether the intervention is feasible for future implementation.

Feasibility and Engagement

Feasibility will be assessed according to **process, resource, management, and scientific** indicators (Adamson et al., 2016; Learmonth & Motl, 2018).

Process feasibility assesses participant recruitment. A recruitment rate (dividing the total number of participants enrolled by the number of participants contacted) and eligibility rate (number of potential participants excluded from the total number of interested participants) will be calculated. We will aim to have a recruitment rate of 60% and eligibility rate of 55% as reported by Jeske and colleagues (2020) in a physical activity intervention for individuals living with SCI.

Resource feasibility assesses participation and monetary requirements of the study. Participation will be examined through retention rate (number of participants who completed at least some part of the intervention from those who were randomized) and adherence rate (number of participants who completed testing and follow-up measures). We will aim to have a retention rate of 90% (physical activity intervention for individuals with SCI; Jeske et al., 2020) to 100% (used at least one part of mobile health application; Smith et al., 2017) as reported by similar interventions. We will aim to have an adherence rate of 81-90% (Allin et al., 2020). We will assess the costs of the study as calculated by the total cost for producing the software and app, participant remuneration, and potential cost of the health behaviour coach.

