Management feasibility assesses data management and safety reporting during the study. We will record the IRB approval time according to the total number of days from submission to approval notification including any amendment details as necessary. Next, we will report staff preparation and reporting time calculated as the time to: recruit partners, conduct partner interviews, analyze recommendations, recruit participants, liaise with participants (e.g., group allocation, answering questions), and enter and check all participant data (i.e., total minutes). Missing data items (i.e., questions not answered for testing) will be monitored for baseline and follow-up assessments.

Scientific feasibility assesses the safety, burden, and treatment effect of the study. Safety will be recorded as the number of health problems experienced by the participants over the course of the intervention. Demographic information will be established via a self-report questionnaire. We will describe measures for assessing participant satisfaction and burden below in the qualitative measures section. Compliance with the intervention will be calculated according to the number of participants who complete each weekly module. Although participant compliance is high for traditional physical activity interventions for people with SCI (88% to 91.7%; Brawley et al., 2013; Jeske et al., 2020), we expect much lower compliance for an app-based intervention. Notably, one intervention states that compliance ranges from 16% to 100% depending on the module. As such, we expect to see different compliance rates throughout the course of the intervention. Finally, treatment effects will be assessed according to the quantitative measures listed below.

Engagement with the app will be measured in different ways. First, we will measure compliance as stated above. Next, we will assess the number of times logged into the app over the course of 8-weeks. Finally, we will look at how long each participant spends logged into the app during each module. Previous research suggests that web users spend significantly longer on

interventions compared to app users, but app users log into interventions significantly more times than web users (Morrison et al., 2018).

Outcome Measures

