The Leisure-Time Physical Activity Questionnaire-SCI (LTPAQ-SCI): The LTPAQ-SCI is a self-report recall measure administered by the student investigator to understand the frequency, duration, and intensity of LTPA performed over the previous seven days (Martin [name] et al., 2012).

The Measure of Experiential Aspects of Participation (MeEAP): The MeEAP is a questionnaire to assess the six experiential aspects of participation (i.e., belongingness, meaning, mastery, engagement, challenge, and autonomy) across life domains (Caron et al., 2019). The

MeEAP is completed separately for each life domain with 12-items. Participants will be asked to complete the MeEAP for the exercise and sport domains only, for a total 24 items. Participants respond using a 7-point Likert type scale ranging from 1 (strongly disagree) and 7 (strongly agree).

The Craig Handicap Assessment and Reporting Technique – Short Form (CHART-SF):

The CHART-SF will be used to assess employment and financial resources (Whiteneck et al., 1992). This questionnaire allows for both multiple choice and fill-in-the-blank answers. The CHART-SF will be modified to 2-items for the current study to only assess employment hours and financial earnings.

Acceptability

Semi-Structured Interview: After the final measurements at 8-weeks, participants from the intervention group will be invited to participate in an interview. This interview will allow the participant to provide feedback on the intervention with respect to satisfaction, burden, usability, and recommendations for future improvement. Previous interventions report high levels of satisfaction (Brawley et al., 2013), usability, and acceptability (Allin et al., 2020).

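### The Summary promises a quantitative evaluation of acceptability, but the plan describes only an interview, and it is unclear whether those who miss the week-8 survey are invited to it

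*Combined protocol and SAP*

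**What the plan says.** The Summary (Objectives) separates a qualitative evaluation of the program, objective (b), from objective (c), which is to "quantitatively evaluate the engagement, acceptability, and feasibility, in addition to behaviour change factors" and further outcomes. Purpose & Hypothesis restates the aim without the word quantitatively, then says: "The primary hypothesis is that the program will be deemed an acceptable and feasible method".

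Section 2, Feasibility and Engagement, states that "Scientific feasibility assesses the safety, burden, and treatment effect of the study", but two sentences later hands part of this on: "We will describe measures for assessing participant satisfaction and burden below in the qualitative measures section". Under its Acceptability heading, section 2 lists one measure, a semi-structured interview covering satisfaction, burden, usability and suggested improvements. Section 3 counts and names eight online questionnaires. Section 8 plans mixed models for the quantitative outcomes and inductive content analysis for the interviews.

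On who is interviewed, the Summary (Study Design/Methods) says: "After completing the final assessments at 8-weeks, participants in the intervention group will be invited to participate in an interview". Section 3 likewise places the invitation after completion of the final online survey. Section 2 (Acceptability) gives timing only: "After the final measurements at 8-weeks, participants from the intervention group will be invited to participate in an interview". Section 5 pays for the interview separately from the questionnaires.

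**The concern.** The interview serves objective (b), so objective (c) needs something more. Engagement and feasibility have numeric indicators; acceptability appears to have none. Following the text as written would therefore not deliver the acceptability part of (c), and half of the primary hypothesis would have no numerical summary. Ratings of this kind cannot be collected once the 8 weeks are over.

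The interview is also the only source on satisfaction, usability and burden. If the invitation depends on completing the week-8 survey, those who miss it are absent from that evidence. If they also like the program less, the evidence tilts favourable. Retention, module compliance and log-ins do count these people, but the plan labels them feasibility or engagement, and they do not record satisfaction or burden.

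**Working it through.** The plan has no sample-size or power figure to reproduce on this point. The check is mainly a comparison of the text.

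**1. Each term of objective (c) against its measures**

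| Term in (c) | Numeric measure in the plan | Where |
|---|---|---|
| Engagement | module compliance, log-ins, time in app | section 2, Feasibility and Engagement |
| Feasibility | recruitment 60%, eligibility 55%, retention 90-100%, adherence 81-90%, and others | section 2, Feasibility and Engagement |
| Acceptability | none; interview only | section 2, Acceptability; section 8 |

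**2. Questionnaires named in section 3**

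They cover psychological needs, motivation, social support, action control, determinants of physical activity, leisure-time physical activity (LTPAQ-SCI), quality of participation and employment. That makes 8, matching the stated number. All are described as measuring the participant; 0 of 8 is described as rating the program.

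**3. Present survey length (section 2)**

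18 (psychological needs) + 7 (social support) + 15 (motivation) + 24 (modified determinants questionnaire) + 6 (action control) + 24 (participation, two domains) + 2 (employment) = 96 items. The length of the LTPAQ-SCI is not given, so 96 is a minimum.

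**4. How many could be missed, on the literal reading of the invitation**

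Inputs: 10 participants in the intervention arm (section 3) and the adherence target of 81-90% (section 2). The target covers the whole trial. Applying it to week 8 in one arm, with participants independent, is an assumption.

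- Expected number missed, 10 × (1 − a): at 90%, 10 × 0.10 = 1.0; at 81%, 10 × 0.19 = 1.9.
- Chance of at least one missed, 1 − a^10: at 90%, 1 − 0.90^10 = 0.651; at 81%, 1 − 0.81^10 = 0.878.
- Chance of three or more missed (binomial, n = 10): about 7% at 90% and 29% at 81%. The figures of 1.0 and 1.9 are therefore averages, not upper limits.

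**The case against.** The strongest reply is that the mismatch rests on one word in a Summary. Purpose & Hypothesis omits quantitatively, and sections 2, 3 and 8 consistently treat acceptability through an interview. That is a legitimate choice for a 20-person pilot, and the primary hypothesis does not demand a rating or a threshold. Much of this stands: the word may be a drafting slip, and deleting it would reconcile the text. But the Summary sets out (b) and (c) as separate objectives, so the team has to decide which plan it means, and decide before week-8 data are collected.

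Second, the heading "2. MEASURES (Appendix A)" points to an appendix that was not available and might hold a further scale. This cannot be excluded. It looks unlikely, because section 2 assigns satisfaction and burden to the qualitative measures, section 3 names exactly eight questionnaires, and section 3 cites Appendix A for feasibility metrics.

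Third, completing may describe sequence and not a condition. This also stands. A reader might infer that the plan excludes non-completers from the interview. No section says so, section 2 gives timing only, and the interview payment is not tied to the survey. Nor does leaving the app mean losing the invitation: someone who stops using it but answers the emailed survey would be asked on any reading.

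**Conclusion.** The point holds as a gap in specification, minor to moderate in weight. In the text available, objective (c) promises a quantitative evaluation of acceptability for which there is no measure and no numerical summary. The invitation rule for those who miss the week-8 survey is unstated. On the literal reading, an average of 1.0 to 1.9 of 10 would be missed, with a 65% to 88% chance of at least one. This rests on the whole-trial adherence target holding at week 8 in that arm and on independence between participants.

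Two stronger conclusions are not supported. A reader might infer that the acceptability findings will be biased in the program's favour. That needs non-completers to be left out and to be less satisfied; the first is one reading and the second is an assumption. A reader might also turn the missed interviews into an inflated percentage of favourable views, but the plan computes no such percentage: section 8 has only content analysis.

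**What to change.** 1. Add a short set of fixed items on satisfaction, burden and usability, with a stated response scale, to the existing week-8 Qualtrics survey for the intervention arm. Send the same items alone, as a separate short link, to anyone who leaves or does not answer. List them in section 2 (both Feasibility and Engagement, and Acceptability) and in section 3. In section 8, add a descriptive summary beside the interviews: the count out of all randomised to the intervention, an exact 95% confidence interval and the number of non-responders, with no pass/fail test.

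2. In the Summary, section 2 (Acceptability) and section 3, state that all participants randomised to the intervention are invited to the interview at week 8 or on leaving the program, whether or not they complete the week-8 survey, except those who decline further contact. Report how many non-completers were invited and how many were interviewed.

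If step 1 is not adopted, remove acceptability from objective (c) so that the Summary matches the interview-only plan, and keep step 2.

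**Cost.** One item per topic adds 3 to at least 96, or about 3% (3/96 = 3.1%), for 10 people. One or two extra interviews cost $10 to $20 at the $10 rate in section 5, plus interviewing and transcription time. The separate link has to be built and tracked, and an ethics amendment may be needed. Some non-completers will answer neither request. With 10 people the interval stays wide (as an illustration, 8 of 10 gives 44% to 97%), so the rating describes acceptability and does not test it.

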1. BACKGROUND AND PROGRAM RATIONALE

1.1 *Physical activity among individuals with SCI who ambulate*

Individuals living with SCI who ambulate participate in significantly less leisure-time physical activity (LTPA) than individuals with SCI who use a wheelchair (Martin [name] et al., 2010). Participation in low levels of LTPA may mean that ambulators with SCI are not obtaining the associated health benefits, such as increased cardiovascular fitness, or reduced pain and fatigue (DiPiro et al., 2016). This group may not be participating in LTPA due to unique barriers such as pain (Roberton et al., 2011), lack of group identity (Martin [name], Papathomas, et al., 2017), lack of interest (Scelza et al., 2005), and lack of evidence-informed interventions to increase the quantity of LTPA participation. Recently, a cross-sectional study found that action and coping planning, goal conflict, and skills predict LTPA behaviour among ambulators with SCI ([name] & Martin [name], In press). Interventions informed by behaviour change theory that use strategies to target these behaviour change constructs could be valuable when aiming to increase the quantity of LTPA among ambulators with SCI.

1.2 *Quality participation in physical activity*

There is also a need to understand how to improve the quality of LTPA participation (i.e., subjective perceptions and experiences; Hammel et al., 2008) among ambulators with SCI. The quality of LTPA experiences may be important for improving well-being, health (Labbé et al., 2019; McLean et al., 2014) and maintaining LTPA participation (Fong et al., 2020). A qualitative study using a pragmatic approach recently examined subjective experiences in LTPA among this population, informed by the Quality Participation Framework (Martin [name], Evans, et al., 2017) and the Quality Parasport Participation Framework (Evans et al., 2018) ([name] et al., In preparation). The study identified intrapersonal, social, program, and physical conditions that influence quality elements in LTPA (i.e., belongingness, meaning, mastery, engagement, challenge, and autonomy) ([name] et al., In preparation). These conditions may be targeted in an intervention to increase the quality of LTPA through behaviour change techniques such as goal setting (Michie et al., 2011). Behavioural support can increase quality through understanding the context of physical activity participation for ambulators with SCI, including experiences of ableism, feeling sidelined, and invisibility ([name] et al., In preparation).

1.3 *Physical activity intervention design and implementation*

Developing and implementing effective physical activity interventions requires a multifaceted approach. Using the person-based approach (Yardley, Ainsworth et al., 2015) in combination with evidence, theory, and integrated knowledge translation (IKT, i.e., involving end-users throughout the research process; Graham et al., 2006) offers a unique and potentially impactful method for physical activity intervention development. To begin, the person-based approach aims to offer the groundwork for developing interventions which account for the context, perspectives, and lives of individuals who use them through mixed methods research (Yardley, Ainsworth, et al., 2015). As such, the person-based approach aligns well with IKT with the goal of involving end-users, and also with the concurrent use of theory and evidence (Yardley, Ainsworth et al., 2015). The person-based approach identifies strategies for

intervention planning, design, and development to ensure acceptability and feasibility for end-users throughout and is thus ideal for digital health interventions (Yardley, Ainsworth, et al., 2015; Yardley, Morrison et al., 2015).

Interventions that are evidence- and theory-based and use IKT can improve physical activity outcomes among individuals with SCI (e.g., Ma et al., 2020). One such theory is self-determination theory (SDT), which suggests that three basic needs are required for motivation and well-being: autonomy, competence, and relatedness (Ryan & Deci, 2000). SDT also posits that self-determined motivation lies on a spectrum from extrinsic (controlled) to intrinsic (autonomous) (Ryan & Deci, 2000). SDT aligns well with evidence from the study by [name] and Martin [name] (In press) as planning can increase autonomous motivation (Sweet et al., 2017) and increasing competence through self-efficacy is a main goal (Ryan & Deci, 2000). Indeed, interventions can use behaviour change techniques that target SDT constructs (Sweet et al., 2017). Furthermore, SDT is inherently aligned with the Quality Participation Framework (Martin [name], Evans, et al., 2017), as more intrinsically motivating (or self-determined) physical activities are likely to be higher quality. Finally, recent evidence suggests that an 8-week SDT-informed telerehabilitation intervention can increase motivation and physical activity levels among individuals with SCI (Chemtob et al., 2019). Accordingly, using SDT may be a useful theory for informing a physical activity intervention that aims to increase quantity and quality of LTPA participation. Thus, we will use SDT as the framework to guide this intervention. Specifically, intervention components will target the three basic psychological needs in an effort to increase autonomous motivation to participate in LTPA (Ryan & Deci, 2000).

PURPOSE & HYPOTHESIS

Primary objective: The purpose of this project is to: (a) collaboratively develop and implement an intervention delivered through a mHealth app for persons with SCI who walk to increase the quantity and quality of physical activity, (b) evaluate the engagement, acceptability, and feasibility of the aforementioned intervention, and (c) assess primary outcomes of basic psychological needs, autonomous motivation, leisure-time physical activity levels, quality of physical activity participation, and employment.

Hypotheses: The primary hypothesis is that the program will be deemed an acceptable and feasible method of improving physical activity participation among individuals with SCI who ambulate. A secondary hypothesis is that the program will improve basic psychological needs and autonomous motivation to participate in LTPA. A tertiary hypothesis is that the program will increase leisure-time physical activity levels, quality of physical activity participation, and employment.

2. MEASURES (Appendix A)

The following section on Feasibility and Engagement will not require any additional effort or information from participants, but rather assesses the study progression to understand whether the intervention is feasible for future implementation.

Feasibility and Engagement

Feasibility will be assessed according to **process, resource, management, and scientific** indicators (Adamson et al., 2016; Learmonth & Motl, 2018).

Process feasibility assesses participant recruitment. A recruitment rate (dividing the total number of participants enrolled by the number of participants contacted) and eligibility rate (number of potential participants excluded from the total number of interested participants) will be calculated. We will aim to have a recruitment rate of 60% and eligibility rate of 55% as reported by Jeske and colleagues (2020) in a physical activity intervention for individuals living with SCI.

Resource feasibility assesses participation and monetary requirements of the study. Participation will be examined through retention rate (number of participants who completed at least some part of the intervention from those who were randomized) and adherence rate (number of participants who completed testing and follow-up measures). We will aim to have a retention rate of 90% (physical activity intervention for individuals with SCI; Jeske et al., 2020) to 100% (used at least one part of mobile health application; Smith et al., 2017) as reported by similar interventions. We will aim to have an adherence rate of 81-90% (Allin et al., 2020). We will assess the costs of the study as calculated by the total cost for producing the software and app, participant remuneration, and potential cost of the health behaviour coach.

Management feasibility assesses data management and safety reporting during the study. We will record the IRB approval time according to the total number of days from submission to approval notification including any amendment details as necessary. Next, we will report staff preparation and reporting time calculated as the time to: recruit partners, conduct partner interviews, analyze recommendations, recruit participants, liaise with participants (e.g., group allocation, answering questions), and enter and check all participant data (i.e., total minutes). Missing data items (i.e., questions not answered for testing) will be monitored for baseline and follow-up assessments.

Scientific feasibility assesses the safety, burden, and treatment effect of the study. Safety will be recorded as the number of health problems experienced by the participants over the course of the intervention. Demographic information will be established via a self-report questionnaire. We will describe measures for assessing participant satisfaction and burden below in the qualitative measures section. Compliance with the intervention will be calculated according to the number of participants who complete each weekly module. Although participant compliance is high for traditional physical activity interventions for people with SCI (88% to 91.7%; Brawley et al., 2013; Jeske et al., 2020), we expect much lower compliance for an app-based intervention. Notably, one intervention states that compliance ranges from 16% to 100% depending on the module. As such, we expect to see different compliance rates throughout the course of the intervention. Finally, treatment effects will be assessed according to the quantitative measures listed below.

Engagement with the app will be measured in different ways. First, we will measure compliance as stated above. Next, we will assess the number of times logged into the app over the course of 8-weeks. Finally, we will look at how long each participant spends logged into the app during each module. Previous research suggests that web users spend significantly longer on

interventions compared to app users, but app users log into interventions significantly more times than web users (Morrison et al., 2018).

Outcome Measures

The Psychological Need Satisfaction in Exercise Scale: This 18-item scale assesses the satisfaction of the psychological needs for exercise using a 6-point Likert scale ranging from 1 (false) to 6 (true) (Wilson et al., 2006). A mean can be calculated for each psychological need (6-items each for autonomy, competence, and relatedness) with a higher score representing greater satisfaction of that need. The scale will be adapted by replacing “exercise” with “physical activity”.

Social Support: Social support will be measured using a modified version of Sallis’ social support questionnaire (Sallis et al., 1987). The 7-item survey uses a 6-point Likert-type scale and assesses emotional support (3 items) and practical support (4 items). A similar version has been used in a similar intervention among individuals living with SCI and is sensitive to change in physical activity behaviour (Ma et al., 2019).

The Treatment Self-Regulation for Exercise Scale (TSRES): The TSRES assesses autonomous and controlled motivation. The 15-item TSRES uses a 7-point Likert scale ranging from 1 (not at all true) to 7 (very true) to assess why one *would* engage in exercise activities (Levesque et al., 2007). The scale will be adapted by replacing “exercise” with “physical activity”.

The Determinants of Physical Activity Questionnaire (DPAQ): This 33-item questionnaire is derived from Taylor et al. (2013) and based on the components of the Theoretical Domains Framework (Michie et al., 2008). This questionnaire aims to understand the behaviour change factors that influence LTPA among ambulators with SCI. A modified version will be used to assess the following domains targeted in the intervention: Knowledge, Beliefs about Capabilities, Skills, Social Influences, Beliefs about Consequences, Action Planning, Coping Planning, and Goal Conflict (24-items).

Action Control: Action control will be assessed with six items that ask participants to indicate the extent to which they self-monitor their physical activity (1 = definitely false; 7 = definitely true) (Sniehotta et al., 2005). The scale has been demonstrated to be valid and reliable in individuals living with SCI. The scale will be adapted by replacing “exercise” with “physical activity”.

The Leisure-Time Physical Activity Questionnaire-SCI (LTPAQ-SCI): The LTPAQ-SCI is a self-report recall measure administered by the student investigator to understand the frequency, duration, and intensity of LTPA performed over the previous seven days (Martin [name] et al., 2012).

The Measure of Experiential Aspects of Participation (MeEAP): The MeEAP is a questionnaire to assess the six experiential aspects of participation (i.e., belongingness, meaning, mastery, engagement, challenge, and autonomy) across life domains (Caron et al., 2019). The

MeEAP is completed separately for each life domain with 12-items. Participants will be asked to complete the MeEAP for the exercise and sport domains only, for a total 24 items. Participants respond using a 7-point Likert type scale ranging from 1 (strongly disagree) and 7 (strongly agree).

The Craig Handicap Assessment and Reporting Technique – Short Form (CHART-SF):

The CHART-SF will be used to assess employment and financial resources (Whiteneck et al., 1992). This questionnaire allows for both multiple choice and fill-in-the-blank answers. The CHART-SF will be modified to 2-items for the current study to only assess employment hours and financial earnings.

Acceptability

Semi-Structured Interview: After the final measurements at 8-weeks, participants from the intervention group will be invited to participate in an interview. This interview will allow the participant to provide feedback on the intervention with respect to satisfaction, burden, usability, and recommendations for future improvement. Previous interventions report high levels of satisfaction (Brawley et al., 2013), usability, and acceptability (Allin et al., 2020).

